### Abbreviations

AE	Adverse Event
AKI	acute kidney injury
AUC	area under the concentration curve
CHF	Congestive Heart Failure
CKD	chronic kidney disease
CPK	creatine phosphokinase
CRF	Case Report Form
DAC	data adjudication committee
eGFR	estimated Glomerular Filtration Rate
ePV	estimated plasma volume
eTBV	estimated total blood volume
EOS	end of study
GFR	Glomerular Filtration Rate
hcg	human chorionic gonadotropin
IB	Investigators Brochure
ICU	Intensiv Care Unit

IMP	investigational medicinal product
ITT	Intent to treat Population
mGFR	Measured Glomerular Filtration Rate
mPV	measured Plasma Volume
mTBV	measured total blood volume
NYHA	New York Heart Association
PPP	Per protocol population
PV	Plasma Volume
SAE	Serious Adverse Event
TBV	total blood volume
TEAE	treatment-emergent adverse event
VFI	Visible fluorescent injectate (FD004)
WOCBP	Women of child-bearing potential

Study Physician / member of the trial team
 
Trial Statistician
	

Hypotheses
	
It is hypothesized that utilizing the FAST PV and mGFR Technology™ is safe and functional in CHF patients. It is also hypothesized that quantitative measurements of intravascular plasma volume status and GFR will differ from standard clinical assessments and estimating equations, and that clinical decision making would have been improved in a subpopulation of patients had the quantitative measurements delivered by the FAST PV and mGFR Technology™ been available to the physician during the course of care.


Rationale
	
Previous clinical studies have shown the FAST technology to be safe and functional in patients with chronic kidney disease (CKD) and in healthy subjects. The technology has not been studied in CHF patients. In previous clinical studies, the technology has been demonstrated to accurately measure PV and mGFR in patients with CKD and healthy patients when compared to other clinical techniques including, estimated glomerular filtration rate (eGFR) calculations, Iohexol clearance and Nadler's formula. Additionally, previous studies have shown that the concentration of the PV marker remains relatively constant during the first two hours after injection, given that this high-molecular weight marker is predicted to exclusively occupy the intravascular compartment and exhibit a long half-life.
 
In this study, the safety and functionality of the FAST Technology will be evaluated in CHF patients. The non-clinical and clinical history of the product provides confidence that the

	
technology will be well tolerated and function correctly in the CHF population.
 
The blood samples are timed to maximize the information gathered during the study. In addition to measurements of PV and GFR, FAST will determine the technology's functionality by comparing the concentration of the PV marker at the 15, 30 and 60 minute time points. It is not believed that the plasma volume will change significantly within that time period and thus the concentration of the PV marker should remain relatively constant.

Study medication (IMP) / Therapeutic strategy	
Visible fluorescent injectate (VFI) (FD004), Powder for Solution for Injection, 47 mg. VFI is diluted with Water for Injection and a total of 3 mL of VFI is administered by bolus injection. There is 47 mg of VFI administered in this 3 mL dose (35 mg of FD001 and 12 mg of FD003). VFI is dosed on Day 1 and Day 3 approximately 48 hours apart.

Study design	
This is an investigator-initiated, one-armed phase II clinical study designed to evaluate the safety and function of the FAST PV and mGFR Technology in patients with CHF. Data from the FAST PV and mGFR Technology will not be evaluable by the treating physician, but will be made available to the study investigators and to an adjudication committee.
 
Patients enrolled in the study will be administered the Day 1 Dose of VFI after enrollment and the Day 3 dose approximately 48 hours after the initial dose.
 
After consenting to be enrolled in the study, patients meeting the enrollment criteria will receive a single dose of VFI (Day 1). Blood draws (3 mLs) will be collected pre-dose and at 15 (<math>\pm 5</math> minutes), 30 (<math>\pm 5</math> minutes), 60 (+30 minutes), and 180 (+120 minutes) minutes post-dose which will be subsequently used to determine the patient's blood volume and mGFR using the FAST PV and mGFR Technology. Patients will be treated according to standard of care throughout the time of their hospitalization. A second dose of VFI will be administered 48 (<math>\pm 5</math> hours) hours after the initial dosing (Day 3). Again, blood draws (3 mLs) will be collected at 15 (<math>\pm 5</math> minutes), 30 (<math>\pm 5</math> minutes), 60 (+30 minutes), and 180 (+120 minutes) minutes post-dose
 
In addition, study-related blood samples will be obtained on days 1, 2, 3, 4, 5 to measure serum creatinine (days 1-5), hematocrit (days 1, 3), and N-terminal pro-brain natriuretic peptide (NT-pro-BNP), Creatine phosphokinase (CPK), Alanine aminotransferase (ALT), Aspartate aminotransferase (AST) (U/l), Alkaline phosphatase (AP), Bilirubin total and direct, International Normalized Ratio (INR) (days 1,3,5), and

	
will be stored for future testing of additional parameters in the research fields of acute decompensated heart failure and acute kidney injury.
 
Furthermore, the available laboratory values from routine clinical practice (see Table 1) will be entered in the Case Report Form (eCRF).
 
On days 1-5, the patient will be asked to complete a Patient Symptom Assessment Sheet (see Annex D).
 
On days 1 and 3, the treating physician will be asked to complete a very brief survey (Annex E) to provide a qualitative assessment of the patient's perceived intravascular volume status and renal function. The study physician will conduct a non-invasive clinical assessment of the patient (including e. g. body weight, height, edema grade, blood pressure, heart rate, respiratory rate, jugular venous distension assessment, oxygen saturation) on days 1-5.
 
In addition, the study physician will record in the eCRF detailed information regarding diuretics dosage, i. v. fluid application, and requirement of renal replacement therapy as ordered by the clinicians in the hospital.
 
Laboratory values and assessments (see Table 1) will be captured on each day that the VFI is administered and these data will be entered into the eCRF. Any AEs determined by the investigator to be related or possibly related to the VFI will be captured. Patients will also receive a follow up phone call 7 days (<math>\pm 2</math> days) after the second dose of VFI was administered, and a second follow up call 30 days after the second dose of VFI was administered. This second phone call will serve as the end-of-study (EOS) follow-up call. Any AEs determined by the investigator to be related or possibly related to the VFI will be captured during the follow up calls and will be followed to resolution. Additionally, in-person follow up visits may be scheduled, as determined by the investigator. During day 1-5, during follow-up phone calls or study visits and through information accessed within the hospital computer system or obtained from treating physicians or relatives, the following study outcomes will be recorded: mortality, length of hospital stay, readmission for heart failure, episodes of acute kidney injury, requirement of fluid resuscitation, episodes of symptomatic hypotension, successful reduction of body weight.
 
Upon conclusion of the study, the recorded clinical data will be provided to an independent data adjudication committee (DAC) in a pseudonymized fashion. The DAC will be asked to

--	---

	
review the available data at the time of the first dosing and the measured GFR and PV data for the first dosing day will be provided. The DAC will then be asked to fill out a survey asking whether the mGFR and PV data would have influenced their treatment decision, and if so, indicate what they would have done differently.
 
Following the evaluation of mGFR and PV data at the time of the initial VFI dose, the mGFR and PV data determined from the second VFI dosing point will be provided to the DAC. The DAC will then be asked to fill out a separate survey asking how the actual measured PV and GFR differ from the clinical assessments, whether the mGFR and PV data would influence their treatment decision, and if so, indicate what they would have done differently.
 
After all assessments have been completed, the DAC will review the results of their analyses and compile a summary report on the secondary endpoints as well as their assessment of the overall impact of the PV and mGFR on clinical decision making.

Total number of patients	We plan to enrol 50 eligible patients. Due to the explorative nature of this phase II study a formal sample size calculation is not possible. However, the sample size of 50 patients is sufficient to guarantee reasonable accuracy with respect to the main objectives of the trial as specified below.
Study population	Male and Female patients aged $\geq 18$ admitted to the hospital ward with a diagnosis of congestive heart failure.
Inclusion criteria	
 
• Written informed consent indicating that they understand the purpose of and procedures required for the study and are willing to participate in the study prior to any study related measures present.
 
• Hospitalized patient with acute decompensated heart failure, diagnosed on the basis of the presence of at least one symptom (dyspnea, orthopnea, or edema) and one sign (rales, peripheral edema, ascites, or pulmonary vascular congestion on chest radiography) of heart failure. Subject: <math>\geq 18</math> years of age.
 
• Male with female partners of childbearing potential gave agreement to practice abstinence or use condoms from enrollment through 90 days after administration of the last dose of study drug present.
 
• Partner of a male patient: Agreement to use a medically acceptable method of contraception (a barrier method, intrauterine device, or hormonal contraception) from enrollment through 90 days after administration of the last dose of study drug present.
 
• Male patient agreed to not donate sperm from enrollment through 90 days after administration of the last dose of study drug present
 
• A female subject is eligible to enter the study if she is:
 

	
 
○ Not pregnant or nursing
 
○ Of non-childbearing potential (i.e., post-menopausal defined as having been amenorrheic for at least 1 year prior to screening, or has had bilateral tubal ligation at least 6 months prior to administration of study drug or bilateral oophorectomy or complete hysterectomy)
 
○ If of childbearing potential (WOCBP), must have a negative urine or serum pregnancy test within 24h prior to drug administration and be using a highly effective means of contraception during study participation and until 1 month after the last dose of study drug. Highly effective contraception methods include: 
 
• Total abstinence (when this is in line with the preferred and usual lifestyle of the subject. Periodic abstinence (e.g., calendar, ovulation, symptothermal, post-ovulation methods) and withdrawal are not acceptable methods of contraception. Combination of any two of the following (i+ii or i+iii, or ii+iii): 
 
(i) use of oral, injected or implanted hormonal methods of contraception or other forms of hormonal contraception that have comparable efficacy (failure rate < 1%), for example hormone vaginal ring or transdermal hormone contraception.
 
(ii) placement of an intrauterine device (IUD) or intrauterine system (IUS)
 
(iii) barrier methods of contraception: condom or occlusive cap (diaphragm or cervical/vault caps)
 
 
 
• In case of use of oral contraception women should have been stable on the same pill for a minimum of 3 months before taking study treatment
 
 
 
• Patient is able to communicate effectively with the study personnel.
 
• Patient is informed of the nature and risks of the study and give written informed consent prior to enrollment.
 

Exclusion criteria	
 
• New or ongoing myocardial infarction or instable angina present at the time of planned study inclusion.
 
• Patient shows evidence of severe infection other than pneumonia, or active internal bleeding (characterized by recent decrease of blood hemoglobin concentration by more than 2 g/dl).
 
• Patient experiences new onset atrial fibrillation.
 
• Patient has an elective surgery planned during the 30 days they are enrolled in the study.
 

	
 
• Patient has a psychiatric disease or a history of illicit drug use that would prohibit them from complying with study requirements
 
• Prior exposure to VFI present.
 
• History of any clinically significant allergic or negative reactions, side effects, or anaphylaxis to fluorescent dyes, or dextran molecules present.
 
• Patient requires intravenous vasodilators or inotropic agents (other than digoxin or digitoxin) for heart failure.
 
• Patient undergoes chronic dialysis (for example peritoneal or hemodialysis) treatments.
 
• Patient is in cardiogenic shock or on vasopressors.
 
• Hypotension as defined by blood pressure <math>\leq 90</math> systolic and/or <math>\leq 50</math> mm Hg diastolic exists.
 
• Patients suffering from significant non-cardiac diseases of other organ systems (e. g. Malignancies, significant neurological diseases)
 
• Patient does not have a working telephone.
 
• Patient is a pregnant or nursing (lactating) women, where pregnancy is defined as the state of a female after conception and until the termination of gestation, confirmed by a positive human chorionic gonadotropin (hCG) laboratory test.
 
• Lack of willingness to storage and disclosure of pseudonymous disease data in the context of the clinical trial present.
 
• Subject has a participation in another interventional clinical trial during this study or within 30 days (or longer) before entry into this trial (as a minimum; 5 x elimination half-life / terminal elimination of an IMP).
 
• Subject is legally detained in an official institution.
 
• Subject is dependent on the sponsor, the investigator or the trial sites.
 

--	---

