	
routine including the following questions:
 
 
○ Would FAST GFR and PV measurements have changed clinical management overall?
 
○ Would the FAST GFR and PV measurement on day 1 have led to applying a different diuretics dosage between day 1-3?
 
○ Would the FAST GFR and PV measurement on day 3 have led to applying a different diuretics dosage between day 3-5?
 
○ Would the FAST GFR and PV measurement on day 1 have led to choosing dialysis/ultrafiltration instead of diuretics escalation between day 1-3?
 
○ Would the FAST GFR and PV measurement on day 1 have led to choosing diuretics escalation instead of dialysis/ultrafiltration between day 1-3?
 
○ Would the FAST GFR and PV measurement on day 3 have led to choosing dialysis/ultrafiltration instead of diuretics escalation between day 3-5?
 
○ Would the FAST GFR and PV measurement on day 3 have led to choosing diuretics escalation instead of dialysis/ultrafiltration between day 3-5?
 

Safety	Adverse events (AEs) will be collected and evaluated as they occur throughout the study.
Discontinuation criteria	
Individual Patient Discontinuation Criteria:  A patient is free to withdraw consent and discontinue participation in the study at any time, without prejudice to further treatment according to standard clinical practice. The investigator may remove a patient if, in the investigator's judgment, continued participation would pose unacceptable risk to the patient or to the integrity of the study data. All procedures for early termination must be completed. Reasons for removal or withdrawal may include:
 
 
• Admission to the ICU prior to either the first or second dose
 
• The patient develops a stated exclusion criterion during the course of study
 
• If the patient experiences an acute anaphylactoid reaction during the course of administering the FAST VFI, administration will stop immediately
 
• Evidence of an anaphylactoid reaction (dyspnea, urticaria, flush, bronchospasm, or severe systemic hypotension)
 
• Administrative decision by the investigator or sponsor
 
• Significant protocol deviation
 
• Patient noncompliance
 
• Safety concern by the investigator or sponsor
 
• Lost to follow-up
 
• Pregnancy
 

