Laboratory values and assessments (see *Table 1*) will be captured on each day that the VFI is administered and these data will be entered into the CRF. Any AEs determined by the investigator will be captured. Patients will also receive a follow up phone call 7 days ( $\pm$  2 days) after the first dose of VFI was administered, and a second follow up call 30 days after the first dose of VFI was administered as an end-of-study (EOS) follow up call. Any AEs determined by the investigator will be captured during the follow up calls and will be followed to resolution. Additionally, in-person follow-up visits may be scheduled as needed.

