### 7.4.3 Final examination

- On the final follow-up visit (phone call) any adverse events will be recorded.

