#### **10.9 Documentation of AEs and SAEs**

All Serious Adverse Events (SAEs) and all Adverse Events (AEs) need to be documented in the patients' clinical file and in the respective CRF pages by the investigator, no matter, whether the investigator suspects a causal relationship to the investigational product or not. The documentation needs to include:

- Duration (start and end dates) or if the event is ongoing an outcome of not recovered/not resolved should be reported
- Action taken regarding study treatment
- Whether other medication or therapies have been taken (concomitant medication/non-drug therapy)
- Its outcome (not recovered/not resolved; recovered/resolved; recovering/resolving, recovered/resolved with sequelae; fatal; or unknown).

Related signs symptoms and laboratory changes should be summarized to a specific disease. The event will be recorded in the CRF. SAEs need to be documented on a separate SAE form.

Out of normal range laboratory data need to be analysed concerning their clinical relevance by the Investigator – and if relevant documented as an AE itself.

All adverse events need to be followed until they subside or stabilize.

The Sponsor will carefully document all SAEs reported by the Investigator. His documentation will be sent to the relevant regulatory authorities and to relevant authorities of other European member states and other contracting states of the EWR agreement, if the study is run in their territory and if they so request.

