### 7.7.2 Safety/Tolerability

#### **Adverse events**

AEs and SAEs will be regarded for safety analysis if they are treatment emergent, i.e. if they were not present prior to the first application of VFI or in case they were present and are worsening after the first application of VFI.

All AEs, whether or not they are considered to be related to treatment are reported.

They are listed by subject providing the following information:

- Age, sex, weight, BMI
- The adverse event (reported term by investigator, MedDRA preferred term, System Organ Class)
- Date of onset
- Duration of the adverse event
- Severity
- Seriousness (serious/non-serious)
- Action taken
- Outcome
- Causality assessment

The adverse events are displayed in summary tables as follows:

- A table of the preferred terms of all AEs will be presented including the number and percentage of subjects in whom at least one event with the respective preferred term (PT) occurred. The PTs will be grouped by MedDRA System Organ Class (SOC) and sorted by frequency.
- Additionally, the number and percentage of subjects in whom at least one event in the respective SOC occurred will be given.
- The tables above will be additionally divided into the defined severity categories grouped by relatedness of the event to VFI.

Every table will be produced for the following AE sets:

- All AEs
- AEs for which a relationship to formula intake was considered to be related by the investigator

Such AEs which were documented as SAEs will be reported in the same way as the AEs.

Every table will be produced for the following SAE sets:

- All SAEs
- SAEs for which a relationship to VFI cannot be ruled out
- All SAEs with outcome death

Additionally, all deaths during the study and deaths that resulted from a process that began during the study are listed by subject.

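### The protocol synopsis limits AE capture to events judged related or possibly related to VFI, against the rest of the protocol and the SAP, so the all-AE tables may be incomplete

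*Protocol*

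**What the plan says.** The Study design row of the protocol synopsis gives the rule for the dosing days as "Any AEs determined by the investigator to be related or possibly related to the VFI will be captured". It repeats the condition for the telephone follow-up, where events judged "to be related or possibly related to the VFI will be captured during the follow up calls and will be followed to resolution".

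The other statements on AE capture carry no causality condition:

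- Synopsis, Safety row: "Adverse events (AEs) will be collected and evaluated as they occur throughout the study".
- Protocol 4.4: "Any AEs determined by the investigator will be captured". SAP 1.2 uses the same sentence, and both documents also leave the follow-up calls unrestricted.
- Protocol 7.4.3: "On the final follow-up visit (phone call) any adverse events will be recorded".
- Protocol 10.9: every AE and SAE goes into both the clinical file and the CRF, "no matter, whether the investigator suspects a causal relationship to the investigational product or not".
- SAP 7.7.2: "All AEs, whether or not they are considered to be related to treatment are reported".

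The primary safety endpoint (protocol 4.1, SAP 7.6) counts AEs and SAEs related to VFI. SAP 7.6 defines these as the grades sure, probable and possible.

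**The concern.** The synopsis makes the investigator's causality judgement a condition for recording an event. Section 10.9 makes it an attribute of an event that is recorded anyway. A site working from the synopsis could therefore leave out non-serious events that 10.9 requires and that the SAP plans to list and tabulate.

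This matters more here than in a controlled trial. There is no comparison arm, so the related-AE frequency rests on the investigator's attribution. That attribution is hard in this population. The anaphylaxis classification in protocol 6.1.1.2 lists nausea, dyspnea, tachycardia and hypotension at grade II. Dyspnea is also a qualifying symptom of heart failure in section 5.1, and section 4.2 names nausea and hypotension among low-output complications. If non-serious events attributed to the disease are not entered, nobody can later review those attributions from the database.

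**Working it through.** No arithmetic applies and the plan states no figure on this point. The check sets the texts side by side.

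1. **Does the qualifier change the rule?** The synopsis and section 4.4 have matching sentences in the same two places: after the dosing-day data, and at the follow-up calls. They differ in the causality phrase, which stands in the synopsis and is absent from 4.4. Read as written, the two texts set different rules.

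2. **Which events fall between the rules?** Section 10.8.1 has six causality grades. The synopsis condition covers sure, probable and possible. It does not cover unlikely, not related or cannot be evaluated. Section 10.9 covers all six.

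3. **Which SAP outputs need the second group?**
   - Primary related-AE and related-SAE frequencies (SAP 7.6): first three grades. Populated under either rule.
   - AE listing by subject, SOC and PT tables for all AEs, and the severity tables grouped by relatedness (SAP 7.7.2): all six grades. Incomplete under the synopsis rule.
   - SAE tables: section 10.11 sends any SAE to the sponsor, and its listed exceptions do not depend on causality. Not directly affected.

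4. **Can causality be reviewed later?** Section 10.10 asks for changes in the suspected relationship to be assessed at each visit once an AE has been detected. That supports review of recorded events. A non-serious event that was never entered has no database record to review.

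5. **Is the conflict settled anywhere?** No section says which text takes precedence, and SAP 8, which lists changes from the protocol, does not mention AE capture.

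**The case against.** The strongest reply is that the synopsis sentences are outliers. The Safety row of the same synopsis is unrestricted, and the dedicated safety section is explicit. Section 10.1 defines an AE without reference to causality and asks for non-directive questioning at each visit. Section 10.7 already requires causality to be assessed for each AE, the three lower grades would have little use under a related-events rule, and SAP 5.1 expects relationship data to be complete. The synopsis sentence does not contain the word 'only'; that exclusion is inferred. All of this stands. It shows that full capture was probably intended and that a site following 10.9 loses nothing. It does not remove two sentences that a site could follow as written.

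A reader might infer three stronger points, which the documents do not support.

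- *That causality could never be re-assessed and omitted events would leave no trace.* Section 10.9 requires entry in the clinical file as well as the CRF, and monitors compare CRF entries with source (12.1.1). SAEs are reported whatever their cause. The synopsis also has mortality, AKI episodes, symptomatic hypotension and heart-failure readmission recorded as outcomes, and symptom sheets are completed on days 1 to 5.
- *That the primary endpoint is directly affected.* Events the investigator judges related are captured under either wording, and the endpoint would rest on the same judgement after the correction.
- *That the first-in-human study shows how much would be lost.* It reports 15 events related to VFI or study procedures, 6 of them to VFI, so 15 − 6 = 9, or 9/15 = 60%, were procedure-related. These 15 were already a subset judged related to something in the study. They arose in healthy adults, at doses of 5, 15, 75 or 150 mg rather than 47 mg, with placebo recipients included. The proportion says nothing about unrecorded AEs in hospitalised heart-failure patients.

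**Conclusion.** The contradiction is real and should be corrected. Its effect is conditional and limited. If a site followed the synopsis, the all-AE listings and the SOC and PT tables would lack some or all non-serious events in three of the six causality grades, and the investigator's attribution of those events could not be reviewed from the database. The primary related-AE count as the investigator judges it, and SAE reporting, are not directly affected.

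The number of events at stake cannot be worked out from the documents; it could be zero if all sites worked to 10.9. The conclusion assumes that the synopsis is read as a working instruction and that its qualifier is taken at face value. Nothing shows that restricted capture was intended.

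**What to change.** Replace the causality-conditioned wording in both synopsis sentences with: *All AEs, regardless of relationship to VFI, will be captured.* This matches 10.9 and costs two sentences of protocol text. It adds no work at sites, because 10.9 already requires it.

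Rewording cannot recover events that were not entered, and SAP 3 describes the 50 patients as already enrolled, with a second hospital added. So also check before analysis that AEs were entered regardless of causality, for example by tabulating AEs by causality grade and centre. This is best done before database lock, when missing entries can still be added from source; the data review meeting in SAP 6 comes after lock. SAP 7.1 notes that one centre has few patients, so an absence of unrelated AEs there is a reason to look at source rather than proof that the filter was applied. Report any centre where only related AEs were recorded as a limitation of the all-AE tables. The cost is one cross-tabulation and, if it raises a question, a targeted source check.
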